2.2 Sample size calculation

The sample size is based on confirming non-inferiority of the primary estimand for the primary endpoint assessed at week 26 using the full analysis set (FAS). Sample sizes are also given for confirming non-inferiority for the primary estimand of the primary endpoint on the per-protocol set.

The primary objective is to confirm the effect of IDegAsp OD versus IGlar OD + IAsp OD in controlling glycaemia in basal insulin-treated subjects with T2DM.

This will be done by comparing the difference between IDegAsp OD and IGlar OD + IAsp OD in change from baseline in HbA_{1c} after 26 weeks to a non-inferiority limit of 0.4%. The non-inferiority limit of 0.4% is aligned with the phase 3a programme and is considered appropriate to ensure a relevant effect of IDegAsp compared to placebo since a superior treatment effect of -0.85% [-1.04; -0.66] of IGlar versus placebo was reported in a placebo controlled clinical trial in T2DM subjects¹. Supplementing IGlar with IAsp OD would further increase the treatment effect compared to placebo.

Formally, let D be the mean treatment difference (IDegAsp OD minus IGlar OD + IAsp OD) in change from baseline in HbA_{1c}. The null-hypothesis of IDegAsp OD inferior by 0.4% or more will be tested against the alternative hypothesis of non-inferiority as given by

$$H_0: D \geq 0.40\% \text{ against } H_A: D < 0.40\%$$

Non-inferiority will be considered confirmed if the upper bound of the two-sided 95% confidence interval for D is strictly below 0.4%. This is equivalent to using a one-sided test of size 2.5%, which means that the Type 1 error rate is controlled at 2.5% level.

Accordingly, the sample size is calculated using a t-statistic under the assumptions of a one-sided test of size 2.5%, a mean treatment difference of 0.0%, a standard deviation of SD=1.3%, and a non-inferiority limit of 0.40%. It is assumed that 15% of the randomised subjects will discontinue randomised treatment before week 26 or have missing data at week 26, and that 10% of the randomised subjects will be excluded from the per protocol (PP) analysis set. The assumptions are based on the results from a phase 3a trial (NN5401-3593).

When estimating the primary estimand for the evaluation of the non-inferiority hypothesis, missing data will be imputed based on in-trial data. A penalty will be added to the change in HbA_{1c} at week 26 for all subjects in the IDegAsp OD arm who discontinued trial product prior to week 26 or who have missing data at week 26. The penalty corresponds to the non-inferiority limit of 0.4%.

In total an expected 15% will have missing on-treatment data at week 26, 10% will not be part of the PP analysis set. This means that $5/90*100\% = 5.56\%$ of the PP analysis set is expected to be non-completers, hence the expected treatment differences (adjusted treatment effect (TE) resulting from the applied penalty) for the non-inferiority hypothesis of the primary estimand is:

- 1) FAS: $0.15*0.4=0.06$
- 2) PP: $0.0556*0.4=0.0222$

The sample size assumptions for TE and the common SD are given in [Table 2-1](#).

From these assumptions, and based on a 1:1 randomisation, the sample size is set to 264 subjects per treatment arm, in total 528 subjects. This will ensure a nominal power of at least 85% for confirming the primary objective based on the FAS as well as on the PP analysis set. The sample size calculation was done using SAS 9.4.

Table 2–1 Assumptions for sample size calculation

Primary Estimand Analysis set	Non-inferiority margin	SD	TE	Adjusted TE	Randomisation Scheme	Required Power
FAS	0.4%	1.3%	0.0%	0.06%	1:1	85%
PP	0.4%	1.3%	0.0%	0.0222%	1:1	85%

Abbreviations: SD = standard deviation; TE = Treatment effect

Table 2–2 Sensitivity of sample size to variations in SD and power

#subjects in total		SD=1.1%	SD=1.2%	SD=1.3%	SD=1.4%
Power 80%	FAS	332	394	462	536
	PP	300	356	416	482
Power 85%	FAS	378	450	528	612
	PP	342	406	476	552
Power 90%	FAS	442	526	618	716
	PP	400	474	556	644
Power 95%	FAS	546	650	762	884
	PP	494	586	686	796

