8.5.2 Laboratory assessments for efficacy

8.5.2.1 HbA_{1c}

The HbA_{1c} result taken at the screening visit (V1) must be available prior to the randomisation visit (V2).

HbA_{1c} is measured regularly during the trial in order to assess glycaemic control and sites will receive individual HbA_{1c} reports for each subject to be used for evaluation and subject training purposes in relation to insulin dose adjustment.

For subjects prematurely discontinuing trial product abbreviated visits (V28a and V40a) should be scheduled at the dates of the originally planned visit 28, if applicable and visit 40 in order to collect samples for HbA_{1c} analysis – refer to flow chart (Section [2](#)).

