2.4 Primary endpoint

Primary statistical analysis for primary estimand

The primary estimand will be estimated based on the FAS using all post baseline HbA_{1c} measurements obtained on planned visits up until week 26, including week 26 measurements from subjects withdrawing from randomised treatment (in-trial observation period), mimicking an ITT scenario. To estimate this estimand for evaluation of non-inferiority of HbA_{1c}, multiple imputation of missing values with separate imputation from each treatment arm will be applied. The use of data from prematurely treatment discontinued subjects in analyses will equalise treatment effects and the inclusion of a penalty equal to the non-inferiority margin will remedy this. Imputation will be done as follows:

- In the first step, intermittent missing values are imputed using a Markov Chain Monte Carlo (MCMC) method, in order to obtain a monotone missing data pattern. This imputation is done for each treatment arm separately and 1000 copies of the dataset will be generated.
- In the second step, for each of the 1000 copies of the dataset, an analysis of covariance (ANCOVA) for each treatment arm with region, sex, previous insulin regimen and previous OAD treatment as categorical fixed effects and baseline HbA_{1c} measurement and age as a covariate will be fitted to the change in HbA_{1c} from baseline to week 8 (visit 10). The estimated parameters and their variance from this model are used to impute missing values at week 8 for subjects in the respective treatment arms based on region, sex, previous insulin regimen, previous OAD treatment, age and HbA_{1c} at baseline.
- In the third step, for each of the 1000 copies of the dataset, an analysis of covariance model with region, sex, previous insulin regimen and previous OAD treatment as categorical fixed effects, and age, baseline HbA_{1c} and HbA_{1c} at week 8 (Visit 10) as covariates is fitted to the change in HbA_{1c} from baseline to week 12 (Visit 14) for each treatment arm. The estimated parameters and their variances from this model are used to impute missing values at week 12 for subjects in the respective treatment arms, based on region, sex, previous insulin regimen, previous OAD treatment, age and HbA_{1c} at baseline and week 8.
- Step three is repeated over the available planned visits, adding one visit at a time until week 26. In each step the model is expanded to include a covariate from the previous visit.

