- Finally, a penalty equal to the non-inferiority margin 0.4% is added to the week 26 (visit 28) HbA_{1c} value for any prematurely treatment discontinued subject in the IDegAsp OD arm, irrespective if the value was retrieved (V28A) data or an imputed value from the sequential imputation, as well as for other subject in IDegAsp arm with missing HbA_{1c} measurement after 26 weeks.

For each of the 1000 (now complete) imputed data sets the change from baseline to week 26 will be analysed using an ANCOVA with treatment, region, sex, previous insulin treatment regimen and previous OAD treatment as categorical fixed effects and baseline HbA_{1c} and age as covariate. The estimates and standard deviations for the 1000 data sets are pooled to one estimate and associated standard deviation using Rubin's rule. From these pooled estimates the confidence interval for the treatment differences and the associated p-value are calculated.

Non-inferiority of IDegAsp OD vs. IGlar OD + IA Sp OD will be considered confirmed if the 95% confidence interval for the mean treatment difference lies entirely below 0.40%. A conclusion on non-inferiority will be based on the FAS and the primary estimand. The addition of the 0.4% penalty in the last imputation step corresponds to the non-inferiority null method, as described by Koch³.

Sensitivity analyses for the primary estimand

The following sensitivity analyses will be performed:

- The primary analysis will be repeated based on the PP analysis set in line with the Committee for Proprietary Medicinal Products (CPMP) Points to Consider (CPMP/EWP/482/99).
- The primary analysis will be repeated on the FAS but without adding the penalty for subjects in the IDegAsp OD arm. The result of this analysis is regarded to give the most fair and unbiased estimate of the difference between the two treatments, in contrast to the primary analysis that due to the penalty is biased in favour of the IGlar treatment.

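### Does the FAS power statement of at least 85% at 528 subjects fail because the penalty's variance and missing week-26 values are left out?

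*SAP*

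**What the plan says.** SAP 2.2 (Protocol 17.2 has the same text) states that "the sample size is calculated using a t-statistic under the assumptions of a one-sided test of size 2.5"%, with "a mean treatment difference of 0.0%, a standard deviation of SD=1.3%, and a non-inferiority limit of 0.40"%. It assumes that "15% of the randomised subjects will discontinue randomised treatment before week 26 or have missing data at week 26". A 0.4% penalty is applied to those subjects in the IDegAsp arm, so the expected FAS difference becomes 0.15 × 0.4 = 0.06%. On these assumptions the total is set at 528, and the section concludes for the FAS: "This will ensure a nominal power of at least 85% for confirming the primary objective based on the FAS". The word nominal is the plan's own.

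The primary analysis (SAP 2.4) uses all week-26 HbA1c values, "including week 26 measurements from subjects withdrawing from randomised treatment (in-trial observation period"), imputes the rest visit by visit within arm, and then "will be analysed using an ANCOVA with treatment, region, sex, previous insulin treatment regimen and previous OAD treatment as categorical fixed effects", together with baseline HbA1c and age. Protocol 8.5.2.1 provides for retrieval of HbA1c after early stopping: "abbreviated visits (V28a and V40a) should be scheduled at the dates of the originally planned visit 28".

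**The concern.** The sentence reads as a guarantee for the confirmatory test, yet the sample size has no margin above the target. The 15% is charged only as a change in the mean. Nothing is added to the variance, although shifting 15% of one arm by 0.4 makes that arm more variable. Nothing is deducted for week-26 values that have to be imputed. The per-protocol row of Table 2-2 is inflated for its 10% exclusions, while the FAS row counts all 264 per arm at full information.

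The 15% is also hard to interpret. In one place it combines stopping treatment with missing data. In another it is put as "In total an expected 15% will have missing on-treatment data at week 26". Because V28a is meant to collect HbA1c from subjects who stop treatment, 15% is not a missing-outcome rate, and no such rate is given. The section also does not say whether SD 1.3% is a raw SD or the residual SD of the ANCOVA. If power were materially below 85%, the trial would run a higher risk than stated of failing to show non-inferiority when the treatments are equal.

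**Working it through.** **Inputs** (SAP 2.2): one-sided 2.5% t-test; SD 1.3%; margin 0.40%; true difference 0; penalty 0.4% on 15% of the IDegAsp arm; 264 per arm.

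**Method.** Distance to the margin: δ = 0.40 − 0.06 = 0.34. With SE = √(s₁²/n + s₂²/n), power is the probability that a non-central t variable with 2n − 2 df and non-centrality δ/SE exceeds the upper 2.5% point of the central t.

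**1. The plan's own figure.**
- n = 264: SE = √(2 × 1.69/264) = 0.11315; δ/SE = 3.005; power 85.07%.
- n = 263: power 84.94%.

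So 528 is the smallest 1:1 total reaching 85%, and every FAS cell of Table 2-2 reproduces. For the PP set, 428 analysed subjects give 85.07%, and 428/0.9 = 476, the table entry. At 90% of 528 (about 475 subjects) PP power is about 88.5%, so that half of the statement has room.

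**2. Penalty variance.** A shift of 0.4 on a fraction 0.15 adds 0.4² × 0.15 × 0.85 = 0.0204 to the IDegAsp arm, if the penalty indicator is uncorrelated with the HbA1c change. Then SE = √((1.69 + 0.0204 + 1.69)/264) = 0.11349, δ/SE = 2.996 and power is 84.86%. The shortfall is 85.00 − 84.86 = 0.14 points. Restoring 85% would take 266 per arm, or four more subjects in all.

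**3. Missing week-26 values (assumed, since no rate is given).** Let m be the fraction missing and r the correlation with the last observed value. Multiply the outcome variance by r² + (1 − r²)/(1 − m) and keep the penalty term.

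| m | r = 0 | r = 0.5 | r = 0.7 | r = 0.9 |
|---|---|---|---|---|
| 5% | 83.0% | 83.5% | 83.9% | 84.5% |
| 15% | 78.8% | 80.3% | 81.7% | 83.7% |

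**4. Gains that the calculation also leaves out (equally assumed).**
- *Covariates.* If 1.3% is a raw SD, 85% is restored when the covariates explain about 0.4% of variance with nothing missing, 3% to 5% with 5% missing (r = 0.7 and r = 0), or about 9% with 15% missing and r = 0.7.
- *Fewer penalised by week 26.* Protocol 6.1 gives 15% as the discontinuation and withdrawal rate for the whole trial (0.85 × 528 = 449 completers), while SAP 2.2 uses 15% at week 26. For a penalised fraction f, δ = 0.40 − 0.4f and the added variance is 0.16 × f(1 − f). With complete data, f = 14% gives δ = 0.344 and power 85.7%; f = 13% gives 86.5%; an even rate over time, f = 15% × 26/38 = 10.3%, gives 88.5%. If every one of that 10.3% were missing with no recovery by imputation, power would be 84.9%.

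**5. Sensitivity already shown.** Table 2-2 lists 536 subjects for 80% power at SD 1.4%. At 528 the same formula gives 79.5%, close to the lowest entry in the table under step 3.

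**The case for a change.** The best argument for a change is that a floor is claimed where the inputs support only about 85%. The penalty variance is a known consequence of the plan's own rule and needs no outside figure. The plan also expects some values to be imputed: SAP 3.1 makes explicit that subjects in the IDegAsp arm who are on treatment but lack a week-26 HbA1c are imputed and penalised. Stating the type of SD and the expected fraction of missing week-26 values would let a reader check the claim, at the price of a few sentences.

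Much of this stands. The omissions are real, 528 has no reserve, and the two missing details would be useful to know. What does not stand is the step to a shortfall that matters. The part that can be computed without assuming a missing fraction is 0.14 points, and even that requires 1.3% to be the SD that applies in the analysis. Everything larger rests on an assumed missing fraction and an assumed recovery by imputation, with the possible gains set to zero. A figure of about 79% is one such scenario. It is not a bound, because a larger SD or more missing data would give less. Printing it in the plan would replace a conditional statement with a less well-founded one.

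**Conclusion.** No change is needed. The sample size and power follow exactly from the stated inputs, and choosing the smallest total that meets a target is ordinary practice. Treating the penalty only as a mean shift is a simplification that costs 0.14 points (85.07% on the plan's inputs, 84.86% against the 85% target), assuming SD 1.3% is the analysis SD before penalty and that being penalised is unrelated to the HbA1c change.

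Whether true power lies above or below 85% cannot be settled from the documents. Missing week-26 values push it down; ANCOVA gain, or fewer than 15% penalised by week 26, push it up, and the offsets needed are small unless many values are missing. Stating the SD type or the missing fraction would record planning detail but would not alter the sample size, margin, estimand, imputation or decision rule. Non-inferiority is decided by the confidence interval, which does not depend on how the power was worded.

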2.3 Definition of analysis sets

The following analysis sets are defined in accordance with the ICH-E9²

- Full Analysis Set (FAS): includes all randomised subjects. In exceptional cases, subjects may be excluded. In such cases the elimination will be justified and documented. The statistical evaluation of the FAS will follow the intention-to-treat (ITT) principle and subjects will contribute to the evaluation “as randomised”.

- Per-Protocol (PP) analysis set: includes all subjects in the Full Analysis Set who fulfils the following criteria:
 - Have not violated any inclusion criteria
 - Have not fulfilled any exclusion criteria
 - Have a non-missing HbA_{1c} at screening or randomisation
 - Have at least one non-missing HbA_{1c} after 12 weeks of exposure
 - Have at least 12 weeks of exposure

Subjects in the PP will contribute to the evaluation “as treated”.

- Safety Analysis Set (SAS): includes all subjects receiving at least one dose of the investigational product or comparator. Subjects in the safety set will contribute to the evaluation “as treated”.
- Trial completer analysis set: Includes all randomised subjects who has attended either V40 on treatment, or V40A, 38 weeks after randomisation according to protocol .
- Treatment completer analysis set: Includes all randomised subjects who have completed the trial without discontinuation from randomised treatment.

Before data are released for statistical analysis, a review of all data will take place to ensure a sufficient data quality and to ensure the planned statistical analysis are applicable. Any data decisions not foreseen in the protocol will be documented before database lock.

Randomised subjects who are lost to follow up and where no exposure information of the investigational product or comparators is available after randomisation will be handled as unexposed.

The decision to exclude any subject or observation from the statistical analysis is the joint responsibility of the study group. The subjects or observations to be excluded, and the reasons for their exclusion will be documented before database lock. The subjects and observations excluded from the analysis sets, and the reasons for this, will be described in the clinical trial report.

Definition of the observation periods:

In-trial: This observation period will include information collected at or after date of randomisation and up to the last scheduled subject-site contact. For subjects who withdraw their informed consent, or is lost to follow-up, the end of the in-trial period is defined as the date of the last scheduled subject-investigator contact (site or phone visit). In case a subject dies during the trial, the date of death will be the end-date of the in-trial observation period regardless of the above defined end-dates. This observation period will be used for estimating the effectiveness estimand.

On-treatment: This observation period is a subset of the in-trial observation period and represents the time period in which a subject is considered exposed to trial product. The period starts on day of the first dose of trial product and ends 7 days after last dose of trial product is taken

2.4 Primary endpoint

Primary statistical analysis for primary estimand

The primary estimand will be estimated based on the FAS using all post baseline HbA_{1c} measurements obtained on planned visits up until week 26, including week 26 measurements from subjects withdrawing from randomised treatment (in-trial observation period), mimicking an ITT scenario. To estimate this estimand for evaluation of non-inferiority of HbA_{1c}, multiple imputation of missing values with separate imputation from each treatment arm will be applied. The use of data from prematurely treatment discontinued subjects in analyses will equalise treatment effects and the inclusion of a penalty equal to the non-inferiority margin will remedy this. Imputation will be done as follows:

- In the first step, intermittent missing values are imputed using a Markov Chain Monte Carlo (MCMC) method, in order to obtain a monotone missing data pattern. This imputation is done for each treatment arm separately and 1000 copies of the dataset will be generated.
- In the second step, for each of the 1000 copies of the dataset, an analysis of covariance (ANCOVA) for each treatment arm with region, sex, previous insulin regimen and previous OAD treatment as categorical fixed effects and baseline HbA_{1c} measurement and age as a covariate will be fitted to the change in HbA_{1c} from baseline to week 8 (visit 10). The estimated parameters and their variance from this model are used to impute missing values at week 8 for subjects in the respective treatment arms based on region, sex, previous insulin regimen, previous OAD treatment, age and HbA_{1c} at baseline.
- In the third step, for each of the 1000 copies of the dataset, an analysis of covariance model with region, sex, previous insulin regimen and previous OAD treatment as categorical fixed effects, and age, baseline HbA_{1c} and HbA_{1c} at week 8 (Visit 10) as covariates is fitted to the change in HbA_{1c} from baseline to week 12 (Visit 14) for each treatment arm. The estimated parameters and their variances from this model are used to impute missing values at week 12 for subjects in the respective treatment arms, based on region, sex, previous insulin regimen, previous OAD treatment, age and HbA_{1c} at baseline and week 8.
- Step three is repeated over the available planned visits, adding one visit at a time until week 26. In each step the model is expanded to include a covariate from the previous visit.
- Finally, a penalty equal to the non-inferiority margin 0.4% is added to the week 26 (visit 28) HbA_{1c} value for any prematurely treatment discontinued subject in the IDegAsp OD arm, irrespective if the value was retrieved (V28A) data or an imputed value from the sequential imputation, as well as for other subject in IDegAsp arm with missing HbA_{1c} measurement after 26 weeks.

For each of the 1000 (now complete) imputed data sets the change from baseline to week 26 will be analysed using an ANCOVA with treatment, region, sex, previous insulin treatment regimen and previous OAD treatment as categorical fixed effects and baseline HbA_{1c} and age as covariate. The estimates and standard deviations for the 1000 data sets are pooled to one estimate and associated standard deviation using Rubin's rule. From these pooled estimates the confidence interval for the treatment differences and the associated p-value are calculated.

Non-inferiority of IDegAsp OD vs. IGlar OD + IA Sp OD will be considered confirmed if the 95% confidence interval for the mean treatment difference lies entirely below 0.40%. A conclusion on non-inferiority will be based on the FAS and the primary estimand. The addition of the 0.4% penalty in the last imputation step corresponds to the non-inferiority null method, as described by Koch³.

Sensitivity analyses for the primary estimand

The following sensitivity analyses will be performed:

- The primary analysis will be repeated based on the PP analysis set in line with the Committee for Proprietary Medicinal Products (CPMP) Points to Consider (CPMP/EWP/482/99).
- The primary analysis will be repeated on the FAS but without adding the penalty for subjects in the IDegAsp OD arm. The result of this analysis is regarded to give the most fair and unbiased estimate of the difference between the two treatments, in contrast to the primary analysis that due to the penalty is biased in favour of the IGlar treatment.
- A tipping point analysis based on the FAS and the primary analysis for the primary estimand will be performed. In this analysis subjects who withdraw from the IDegAsp OD arm or have missing values at visit 26 are assumed to have an effect that is inferior to the de facto effect of IDegAsp OD. The extent of the inferiority (also termed a 'penalty') will be gradually increased to evaluate at which value IDegAsp OD is no longer non-inferior to IGlar OD + IA Sp OD. This penalty value, also known as the tipping point, corresponds to the hypothetical degree of efficacy deterioration in withdrawn subjects that would change the conclusion of non-inferiority.

Primary analysis for the secondary estimand

The secondary estimand will be estimated based on the FAS using post-baseline measurements up to and including week 26 from the on-treatment observation period. To estimate this estimand, the change from baseline in HbA_{1c} after 26 weeks of treatment will be analysed using the mixed model for Repeated Measurement (MMRM) method with a restricted maximum likelihood (REML). The model will include treatment, sex, previous insulin treatment regimen, previous OAD treatment and region as factors and baseline HbA_{1c} and age as covariates, all nested within visit. An unstructured covariance matrix for HbA_{1c} measurements within the same subject will be employed, assuming measurements from different subjects are independent.

The MMRM is a well-established method that accounts for the uncertainty pertaining to missing data. This analysis assumes that the missing data mechanism is missing at random (MAR). Under this assumption the statistical behaviour of the missing data (given the observed responses and model fixed effects and covariates) is assumed to be the same as the observed data.

In a non-inferiority trial the efficacy estimand may be more appropriate than the effectiveness estimand, since it is not confounded by the effects of changing treatment from the randomised treatment to other treatments.

Sensitivity analyses for the secondary estimand

The following sensitivity analyses will be performed:

- The above MMRM analysis will be repeated on the PP using the on-treatment period, as well on the subset of subjects who remains on treatment up until week 26 visit. These analyses will be done to align with the reporting of the phase 3a trials.
- Using the FAS, the change in HbA_{1c} from baseline after 26 weeks of treatment will be analysed using an analysis of variance (ANOVA) method with treatment, sex, previous insulin treatment regimen, previous OAD treatment and region as fixed factors, and age and baseline HbA_{1c} as covariates, and where missing values will be imputed using the Last Observation Carried Forward (LOCF) method. This is done to align with the reporting of the phase 3a trials.

